8.6. Analysis of the Key Secondary Endpoints

Key secondary endpoints will be analyzed according to the hierarchical order specified in Section [8.3.2](#) using a stepwise closed testing procedure to control the overall Type 1 error rate.

Each key secondary endpoint will be analyzed using an ANCOVA model on the ITT-LOCF population. The model will be adjusted for the baseline value (as a continuous covariate) and ERT status (ERT-naïve versus ERT-experienced), as well as baseline age, gender, baseline height, and baseline weight to compare between the 2 treatment groups. The OBSMARGINS (OM) option in the LSMEANS statement will be specified to allow for the use of the observed marginal distributions of the categorical variable rather than assuming a balance among the levels of the categorical variable. The E option will also be specified to check for estimability of LS means. If the LS means are not estimable with the OM option but they are without it, then the analysis without the OM option will be used.

All the relevant estimates from the ANCOVA (including LS means for each treatment group, LS mean difference, standard error of the estimate, 95% CI for the LS mean difference, and p-value for comparing between the 2 treatment groups) will be provided.

The treatment-by-covariate interactions (ie, treatment-by-ERT status, treatment-by-baseline value, treatment-by-age, treatment-by-gender, treatment-by-weight, and treatment-by-height) will be explored. Each interaction term will be explored using a separate ANCOVA model that includes the full set of covariates (ie, treatment, baseline value (as a continuous variable), ERT status, baseline age, gender, height, and weight) as well as the interaction term. Interaction terms with a 2-sided $p < 0.10$ will be further examined clinically. Forest plots will be used to present

the subgroups defined by the baseline covariates. A plot of the LS mean (\pm SE) change from baseline over time will be provided for each key secondary endpoint.

As a supportive analysis, each of the key secondary endpoints will be analyzed using an MMRM analysis on the ITT-OBS population. See further description in Section 8.5.1.1.

For the % predicted FVC, additional supportive and sensitivity analyses will be performed as specified in Section 8.5.1.1 and Section 8.5.1.2, respectively.

If the superiority tests based on the ANCOVA analysis using ITT-LOCF specified for 6MWD and % predicted FVC fail, an informal determination for non-inferiority (NI) for the % predicted FVC will be made based on the 2-sided 95% CI for the treatment difference (new treatment – control). That is, if the lower bound of the 95% CI is equal to or greater than -1.1% (which is the assumed NI margin), then NI would be deemed to have been met.

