15.3.2.3.1. Analyses of the 6MWT

The primary efficacy endpoint (ie, change from baseline to Week 52 in 6MWD) will be analyzed using a parametric analysis of covariance (ANCOVA) model to compare between the new treatment and the control. This model would typically adjust for baseline 6MWD (as a continuous covariate), and the 2 factors used to stratify randomization: ERT status (ERT-naïve vs. ERT-experienced) and baseline 6MWD (75 to < 150 meters, 150 to < 400 meters, \geq 400 meters). However, the baseline 6MWD cannot be used in the model twice (both as a continuous and a categorical variable) due to the expected high point-biserial correlation between them. Thus, the 6MWD continuous variable will remain in the model but the categorical 6MWD will be removed. The ANCOVA model then has terms for treatment, baseline 6MWD (continuous), and ERT status (categorical).

Additionally, potential treatment-by-covariate interactions (ie, TREATMENT-by-ERT-STATUS and TREATMENT-by-BASELINE 6MWD continuous) will be examined. If an interaction term is statistically significant (eg, $p < 0.10$, 2-sided), and there is logical biological interpretation, then the interaction term can potentially be added in the final ANCOVA model that will be used for the primary endpoint analysis. The data would then be analyzed based on the ANCOVA model, and all the relevant estimates (eg, LS means for each treatment group, LS means difference, 95% confidence intervals [CIs] for the LS mean difference, and p-value for comparing between the 2 treatment groups) would be provided.

To support the interpretation of clinical benefit, a composite subject-level response will be defined based on the totality of the treatment outcome data. Subjects will be classified by an ordinal response variable consisting of significant improvement, moderate improvement, or minor/no improvement based on treatment outcomes.

This defines a hierarchical ordinal categorical response variable, for which a continuation logit model will be used to perform separate logistical regression analyses adjusting for baseline factors like duration of prior alglucosidase alfa, gender, and mutation type. The results of these separate logistic regression analysis are then pooled to test the overall null hypothesis that treatment with ATB200/AT2221 is more effective than alglucosidase alfa with respect to either the positive response (ie, significant improvement) or the negative response (ie, minor/no improvement).

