4.3. Sample Size and Power Considerations

The primary endpoint for this study is the change from baseline to Week 52 in the 6MWD.

Using a 2-group t-test with a 1-sided significance level of 0.025 and a 2:1 randomization ratio, a total of 99 subjects (66 subjects in the ATB200/AT2221 group and 33 subjects in the alglucosidase alfa/placebo group) would yield approximately 90% power to detect a clinically meaningful standardized effect size of 0.7 between the 2 groups in a superiority test for the primary endpoint. This calculation was performed using nQuery 8[®].

Assuming a 10% dropout rate (after randomization), a total of approximately 110 subjects were planned to be randomized to ensure 99 evaluable patients.

Details of the sample size justification are described in [Appendix 1](#).

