4.4. Randomization and Stratification

Although this is a multicenter trial, the randomization was not stratified by center. The following 2 risk factors were identified as key prognostic factors, and therefore randomization was stratified according to these:

1. Baseline 6MWD (categorized as: 75 to < 150 meters, 150 to < 400 meters, ≥ 400 meters)
2. ERT status (categorized as: ERT-experienced versus ERT-naïve)

The randomization schedule was generated and administered centrally by Almac Clinical Technologies (Almac), independent of the sponsor's project team. This centralized block

randomization procedure was used to balance the above risk factors, (1) to reduce bias and increase the precision of statistical inference, and (2) to allow various planned and unplanned subset analyses. The randomization ratio was 2:1 (ATB200/AT2221 to alglucosidase alfa/placebo), fixed. Approximately 30 ERT-naïve subjects were planned to be enrolled.

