8.8.5. Proportion Improving on Both 6MWD and % Predicted FVC

The proportion of subjects improving on both 6MWD and % predicted FVC (where definition of improvement is provided in Section 8.7) will be compared between the 2 treatment groups using a logistic regression model adjusting for baseline age, ERT status, gender, baseline height, and baseline weight. The number and percent of subjects improving will be presented for each treatment group, and the p-value for comparing between the 2 treatment groups and the 95% confidence interval for the treatment difference will be calculated from the logistic regression model.

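### Baseline 6MWD, a stratification factor the SAP calls key prognostic, is absent from the models for five of six key secondary endpoints and from the responder models; adding it costs almost nothing and may recover some power.

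*SAP*

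**What the plan says.** SAP 4.4 lists baseline 6MWD (three bands) and ERT status as factors "identified as key prognostic factors, and therefore randomization was stratified according to these".

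The primary MMRM (SAP 8.5.1) includes continuous baseline 6MWD and ERT status, so it reflects both factors.

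For the key secondary endpoints, SAP 8.6 says: "The model will be adjusted for the baseline value (as a continuous covariate) and ERT status (ERT-naïve versus ERT-experienced"), with age, gender, height and weight added. The sample ANCOVA code in SAP Appendix 3 confirms a single BASE term and no separate 6MWD term.

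The only reason given anywhere for leaving out a 6MWD term is in Protocol 15.3.2.3.1: "the baseline 6MWD cannot be used in the model twice (both as a continuous and a categorical variable"). There the band is dropped because the continuous value stays in the model.

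SAP 8.8.5 compares the proportion improving on both 6MWD and % predicted FVC "using a logistic regression model adjusting for baseline age, ERT status, gender, baseline height, and baseline weight". The composite (MDRI) logistic models in SAP 8.7 adjust for ERT status, ERT duration, gender and age. Neither has a baseline 6MWD term.

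**The concern.** The protocol's collinearity argument holds only where continuous baseline 6MWD is already in the model. Of the six key secondary endpoints, that is true of Week 26 6MWD alone. The other five have no 6MWD term at all, and no reason is offered.

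When randomisation is balanced on a prognostic factor that the analysis then ignores, the estimate varies less from trial to trial than the model assumes. The reported SE is too large and the test rejects too seldom.

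This matters most for % predicted FVC, the first test after the primary endpoint in SAP 8.4: if it fails, none of the later key secondary claims can be made. SAP 8.6 also reads an informal FVC non-inferiority result from a 95% confidence bound against -1.1, so interval width counts there too.

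In the responder models the link is more direct. SAP Table 8 defines improvement in 6MWD as at least +6% of baseline, so baseline 6MWD sets each subject's threshold: 9 m at a baseline of 150 m (0.06 × 150) and 24 m at 400 m (0.06 × 400).

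**Working it through.** **The plan's own figure.** SAP 4.3 uses a "2-group t-test with a 1-sided significance level of 0.025 and a 2:1 randomization ratio", with "66 subjects in the ATB200/AT2221 group and 33 subjects in the alglucosidase alfa/placebo group", for "approximately 90% power to detect a clinically meaningful standardized effect size of 0.7". With k = √(1/66 + 1/33) = 0.2132, the noncentral t with 97 df and noncentrality 0.7/0.2132 gives 90.2%. The total reproduces too: 99/0.9 = 110. This sizing is for the primary endpoint; the documents state no design effect for any key secondary.

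**Inputs for the check.** N = 99 split 66/33 (SAP 4.3). The planned ANCOVA has 8 parameters (intercept, treatment, own baseline, ERT status, age, gender, height, weight), leaving 91 residual df, or 90 with baseline 6MWD. Two inputs are assumptions: r, the partial correlation of baseline 6MWD with the endpoint change given the planned covariates, taken from 0 to 0.5; and a standardised effect of 0.6 for illustration.

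**SE.** Adding the term multiplies the reported SE by √(1 − r²) × √(89/88). The second factor, 1.0057, is the cost of one more df and of chance imbalance.

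**Power.** Noncentral t, one-sided 0.025. Without the term: noncentrality 0.6/0.2132 = 2.814, 91 df, power 79.5%. With it: 2.814/√(1 − r²), 90 df.

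| r | SE multiplier | Power with the term |
|---|---|---|
| 0 | 1.006 | 79.5% |
| 0.1 | 1.001 | 79.9% |
| 0.2 | 0.985 | 81.1% |
| 0.3 | 0.959 | 83.1% |
| 0.4 | 0.922 | 85.9% |
| 0.5 | 0.871 | 89.5% |

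Break-even on SE is r = √(1/89) = 0.106. The power column leaves out the chance-imbalance factor. Dividing the noncentrality by 1.0057 as well lowers each entry by under half a point (80.7%, 82.7% and 85.6% at r = 0.2, 0.3 and 0.4).

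**Simulation under stratified blocks** (4,000 runs per setting; blocks of 6, 30% ERT-naïve and 6MWD roughly normal with mean 350 m and SD 110 m, all assumed):

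- At r = 0.3 without the term, the mean reported SE was 0.218 against an actual SD of the estimate of about 0.21. One-sided type I error was 2.1%, within simulation noise of 2.5% (Monte Carlo SE 0.25 points). Adding the term raised power from 77.5% to 80.9%.
- At r = 0.5 the figures were 0.218 against 0.203, and 1.7%, which is clearly below nominal. Power rose from 78.8% to 87.4%.
- At r = 0 the term raised the reported SE by about 0.3% (0.2184 to 0.2190), so 0.6% is on the high side when allocation is stratified.

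**Scale in FVC points.** Assume the residual SD equals the raw 12-month SDs in Protocol Table 3 (6.1, n = 9; 8.7, n = 5). The 95% half-width is then 1.986 × 6.1 × 0.2132 = 2.6 to 1.986 × 8.7 × 0.2132 = 3.7 points. At r = 0.3 it narrows by 4.1%, or 0.11 to 0.15 points.

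**Logistic models.** An illustration with 66/33 subjects, a treatment log odds ratio of 1.1, and log odds of 0.5, 1.0 and 1.5 per SD of baseline 6MWD (all assumed) gave power of 58% to 61%, 51% to 57% and 40% to 52% when the term was added. The SE of the log odds ratio went up (0.495 to 0.519 at 0.5 per SD), but the estimate moved further from zero (1.073 to 1.126). The gain is therefore in power.

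**The case against.** The best counter-argument is that r may be close to zero.

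- What matters is whether baseline 6MWD predicts the change in each endpoint beyond the covariates already planned.
- Age, sex, height and weight are the predictors in the 6MWD reference equations (SAP Appendix 2), so part of its information is already in the model.
- The own baselines of GSGC, MMT lower extremity and PROMIS Physical Function also reflect leg function.
- For FVC, Protocol 6.5 says that respiratory and skeletal muscle decline in no clear order.
- The key prognostic label in SAP 4.4 names no endpoint.

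All of this stands, and it is why the size is given as a range that includes no gain. It does not supply a reason to omit the term, since the cost at r = 0 is about 0.6% in SE.

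Some analyses already involve baseline 6MWD. SAP 8.9 analyses FVC within baseline 6MWD subgroups. SAP 8.5.1.2 words the randomisation-test ANCOVA as adjusted for baseline 6MWD, and Table 7 applies that test to FVC. These are subgroup and sensitivity analyses and leave the main models as they are.

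A reader might infer three stronger things that the documents do not support:

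- **That the key secondary tests are invalid.** They are not: the error is on the conservative side.
- **That any loss at FVC blocks the later claims.** The first gate is the primary 6MWD test, which already has the covariate. After it, only a failed FVC test stops the sequence.
- **That height and weight should leave the 8.8.5 model to make room.** That is a preference and does not follow from the stratification argument.

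**Conclusion.** The omission is confirmed for five of the six key secondary ANCOVAs, for the 8.8.5 responder model and for the MDRI models, and the protocol's stated reason does not cover it. It is a modest efficiency point that is worth correcting because the correction is nearly free.

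With r between 0.2 and 0.4, the reported SE would fall by 1.5% to 8%, and power at an effect of 0.6 would rise by about 1.5 to 6.5 points. Below r of about 0.11 there is nothing to gain. These figures rest on assumed values of r, an assumed effect of 0.6, and 99 analysed subjects. In the logistic models any benefit is in power, with no reduction in the SE of the log odds ratio.

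**What to change.** Before database lock:

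1. Add continuous baseline 6MWD to the SAP 8.6 ANCOVA for % predicted FVC, MMT lower extremity, PROMIS Physical Function, PROMIS Fatigue and GSGC.
2. Add it to the supportive MMRMs for the same five endpoints (SAP 8.5.1.1), and state that it stands alongside the endpoint's own baseline.
3. Add it to the SAP 8.8 ANCOVAs that copy the 8.6 model. The exception is % predicted 6MWD: its own baseline, given age, sex, height and weight, already carries nearly the same information, so the protocol's collinearity reason does apply.
4. Add it to the logistic models in SAP 8.8.5 and 8.7. Height and weight can stay in 8.8.5.
5. Update the sample code in SAP Appendix 3 to match.

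The 6MWD endpoints need no change. The cost is one degree of freedom per model. No imputation is needed, because SAP 6.3.1 reports baseline 6MWD for every ITT subject. If the sponsor prefers to omit the term, the SAP should say why.

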6.3.2. Imputation for Missing Post-baseline Values

For this study, subjects who permanently discontinued the assigned study drug are subsequently discontinued from the study. However, these subjects are required to return for the EOS/ET visit. Efficacy assessments collected at the EOS/ET visit will be used to replace the missing endpoint value at Week 52 in the ITT-LOCF population. That is, the last available observation will be carried forward to replace the missing value at Week 52 (see Section 6.1.4.2).

The MMRM analysis is the primary analysis for the primary endpoint (6MWD), and it will be performed as an ITT-OBS (observed cases) analysis. That is, all available, observed values will be used without imputation, and missing data at Week 52 are not replaced.

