8.2. Testing Statistical Assumptions and Alternative Analysis

Estimated treatment effects such as the least squares (LS) means estimate from linear mixed models (eg, MMRM) and linear model (eg, ANCOVA) are known to be robust against moderate to high deviations from the normality assumption.

The underlying assumptions for the primary efficacy model will still be checked. The MMRM analysis will be used as the primary efficacy analysis for the 6MWD regardless of the results of the normality checks, as the MMRM model is believed to be robust against deviations from normality (Bartlett 2014). The nonparametric randomization-based covariance analysis described in Section 8.5.1.2 will be performed as a sensitivity analysis only if the normality assumption is notably violated with the Shapiro-Wilk test p-value < 0.01. The MMRM analysis assumes that data are missing at random (MAR). For this study, a lot of effort has been (and will continue to be) made to follow up all subjects so as to try to reduce the number of dropouts in the study. Despite all this, it is still possible to have subjects who could not do the 6MWD and/or FVC assessment due to COVID-19 related reasons. In view of the potential impact this can have on the efficacy assessments and analysis, the following analyses are considered:

- The MMRM analysis will be used as the primary efficacy analysis for the 6MWD, based on the ITT-OBS population.
The MMRM analysis uses all available data without imputation for missing data, and the amount of missing data for 6MWD at Week 52 is expected to be small (< 10%). Under these conditions, the MMRM is preferable to the ANCOVA (White, Carpenter et al. 2012; Siddiqui, Hung, et al. 2009).
- The ANCOVA model remains the main analysis for the % predicted FVC and other continuous endpoints, based on the ITT-LOCF population, unless otherwise specified.

The MMRM is a likelihood-based method that does not require a complete dataset; it uses all available data across visits, allowing it to account for differences in variability between visits; and it can model the within-subject variability. These features of the MMRM may be important now in view of the COVID-related interruptions at study sites resulting in delayed visits and make-up assessments, with potentially high between-visit variability. This can also be helpful

given that this study enrolled both ERT-naïve and ERT-experienced subjects who potentially differ in variability.

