8.3.2. Key Secondary Null and Alternative Hypotheses

There are 6 key secondary endpoints in hierarchical order of importance, as follows:

- Change from baseline to Week 52 in sitting FVC (% predicted)
- Change from baseline to Week 52 in the MMT score for the lower extremities
- Change from baseline to Week 26 in 6MWD
- Change from baseline to Week 52 in the total score for the PROMIS – Physical Function
- Change from baseline to Week 52 in the total score for the PROMIS – Fatigue
- Change from baseline to Week 52 in GSGC total score

The null and alternative hypotheses for superiority testing of all the key secondary endpoints are as follows:

H_{0i} : the new treatment is less effective than the control, with respect to the i^{th} key secondary efficacy endpoint

H_{Ai} : the new treatment is more effective than the control, with respect to the i^{th} key secondary efficacy endpoint

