8.5.1.1. Supportive Analyses for the Primary Efficacy Endpoint and % Predicted FVC

The following supportive analyses will be performed:

Table 6: Supportive Analyses for the 6MWD and % Predicted FVC

	Primary Endpoint (6MWD)	% Predicted FVC
1	ANCOVA at Week 52 on ITT-LOCF	MMRM analysis on ITT-OBS
2	Rate of change in 6MWD based on 12-month slopes	Rate of change in % predicted FVC based on 12-month slopes

Abbreviations: 6MWD = 6-minute walk distance; ANCOVA = analysis of covariance; FVC = forced vital capacity; ITT-LOCF = intent-to-treat population with missing data replaced by the last available value; ITT-OBS = intent-to-treat population that includes all available, observed data without any missing data imputation at Week 52; MMRM = mixed-effect model for repeated measures

In addition, note that as a supportive analysis, each of the other key secondary endpoints will be analyzed using an MMRM analysis on the ITT-OBS population as described in Section 8.3.2.

Details for the supportive analyses are as follows:

- MMRM analysis: This is based on the ITT-OBS population, similar to what has been described for the primary endpoint analysis in Section 8.5.1. There is no need to explore the treatment-by-covariate interaction tests in using MMRM as supportive analysis for the key secondary endpoints.
- Rate of change using ANCOVA on the ITT-OBS population based on the 12-month slopes of the 6MWD assessments (ie, change in 6MWD per month), where the slope is estimated for each subject using a simple linear regression of the observed values. The mean slopes are then compared between the 2 treatment groups adjusting for the baseline value (continuous) and ERT status, as well as baseline age, gender, baseline height, and baseline weight. All the relevant LS estimates (including the LS means for each treatment group, LS mean difference, 95% CI for the LS mean difference, SE, and p-value for comparing the 2 treatment groups) will be provided.

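### The informal FVC non-inferiority reading in SAP 8.6 depends on a supportive LOCF ANCOVA for 6MWD, not on the primary MMRM test

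*SAP*

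**What the plan says.** SAP 8.6 sets the condition for the reading: "If the superiority tests based on the ANCOVA analysis using ITT-LOCF specified for 6MWD and % predicted FVC fail". If it is met, non-inferiority of % predicted FVC is judged informally, by whether the lower bound of the two-sided 95% confidence interval is at or above -1.1. The sentence names no visit. It does not say whether one test or both must fail, or which analysis supplies the interval.

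The 6MWD test is defined elsewhere. SAP 6.3.2, 8.2 and 8.5.1 make the MMRM on ITT-OBS the primary analysis, with the significance test at Week 52. SAP 8.4 makes the primary endpoint's test the gate to the key secondary endpoints. The LOCF version appears in Table 6 of SAP 8.5.1.1 as a supportive analysis: "ANCOVA at Week 52 on ITT-LOCF".

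For the key secondary endpoints SAP 8.6 states: "Each key secondary endpoint will be analyzed using an ANCOVA model on the ITT-LOCF population". As a supportive analysis, "each of the key secondary endpoints will be analyzed using an MMRM analysis on the ITT-OBS population". SAP 8.2 calls MMRM preferable to ANCOVA when little 6MWD data is missing and adds: "These features of the MMRM may be important now in view of the COVID-related interruptions at study sites". It also says "The ANCOVA model remains the main analysis for the % predicted FVC and other continuous endpoints", without a reason.

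**The concern.** The non-inferiority statement matters most when superiority has not been shown, so its condition should be the result that decides whether superiority was shown. For FVC it is: the LOCF ANCOVA is the designated FVC test. For 6MWD it is not. The rule therefore permits two odd outcomes. The primary MMRM succeeds but the supportive LOCF ANCOVA fails, and the reading is made. Or the MMRM fails but the LOCF ANCOVA succeeds, and the reading is withheld when it was wanted.

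The wording would fit a plan in which ANCOVA was the primary analysis, as in Protocol 15.3.2.3.1, and may simply not have been updated. That is an inference.

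The second, smaller matter is consistency. The reasons SAP 8.2 gives for MMRM, such as COVID-19 delays and differing variability by ERT status, are not peculiar to 6MWD. Yet the six gate-kept endpoints stay on LOCF with no stated reason.

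**Working it through.** **1. Tests side by side**

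| | Condition in SAP 8.6 | Designated superiority test |
|---|---|---|
| 6MWD | ANCOVA, ITT-LOCF | MMRM, ITT-OBS, Week 52 (SAP 8.5.1) |
| % predicted FVC | ANCOVA, ITT-LOCF | ANCOVA, ITT-LOCF, Week 52 (SAP 8.6) |

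Only the 6MWD row disagrees.

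**2. The plan's own figure.** For 66 + 33 subjects and effect size 0.7, the noncentrality is 0.7 × √(66 × 33/99) = 3.28 on 97 df. Power at one-sided 0.025 is 90.2%, which matches the stated 90%. 99/0.9 = 110 randomized, or about 73 and 37 at 2:1. The plan gives no figure for the non-inferiority condition.

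**3. How often the condition differs.** Simulation, 10,000 trials per scenario, 73 vs 37 subjects, both tests required to fail. Inputs:
- 6MWD SDs 45 (assumed), 52.2, 40.8 and 46.5 m at Weeks 12, 26, 38 and 52, and the shape of the 6MWD course, from Protocol Table 2 (Week 12 assumed).
- FVC mean changes -0.65 (assumed), -1.3, -1.7 and -3.3; SDs 4.0 (assumed), 4.1, 3.9 and 6.1 (Protocol Table 3).
- Assumed: correlation 0.7 between visits and 0.3 between 6MWD and FVC changes; completely random dropout spread evenly after Weeks 12, 26 and 38; no covariates.
- True 6MWD gain 20 m, the minimum important difference in Protocol 6.5.

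| Scenario (10% balanced dropout, FVC difference 0, unless stated) | Condition differs |
|---|---|
| Base case | 5.0% |
| Every dropout has an early-termination visit | 4.1% |
| 5% dropout | 3.5% |
| True FVC difference +3 | 1.8% |
| True 6MWD gain 32.5 m (0.7 SD) | 2.6% |
| True 6MWD gain 0 m | 0.6% |

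Separate runs gave 4.9% to 5.1% for the base case and 1.4% to 1.9% at FVC +3. Both directions occurred: in the base case, 3.7% made after MMRM success and 1.3% withheld after MMRM failure. Monte Carlo SE is about 0.2 percentage points at 5%.

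**4. How often the conclusion changes.** The reading changes a conclusion only if FVC fails superiority but meets the margin. With SD 6.1, SE = 6.1 × √(1/73 + 1/37) = 1.23. The estimate must lie between 1.96 × 1.23 - 1.1 = 1.31 and 1.96 × 1.23 = 2.41.
- True difference 0: P(margin met) = Φ(1.1/1.23 - 1.96) = 0.143. Given failed superiority: (0.143 - 0.025)/0.975 = 0.12. Then 5.0% × 0.12 = 0.6%.
- True difference +3: P(margin met) = Φ(4.1/1.23 - 1.96) = 0.915; P(superiority) = Φ(3/1.23 - 1.96) = 0.683. Given failed superiority: (0.915 - 0.683)/0.317 = 0.73. Then 1.4% to 1.9% × 0.73 = 1.0% to 1.4%.

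Direct simulation counts agree: about 0.5% to 0.6%, and 1.0% to 1.4%. With the ERT-naïve SD of 8.7 at difference 0, SE = 1.76, P(margin met) = 0.091, and the change is 5.0% × (0.091 - 0.025)/0.975 = 0.3%.

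**5. LOCF against MMRM for FVC, true difference 0**
- Balanced 10% dropout: one-sided error 0.025 for both.
- 12% dropout on new treatment, 4% on control (overall (73 × 0.12 + 37 × 0.04)/110 = 9.3%). Expected LOCF shift: 0.08 × (3.3 - mean(0.65, 1.3, 1.7)) = 0.17 points. Approximate error: 1 - Φ(1.96 - 0.17/1.23) = 0.034. Simulated LOCF error was up to about 0.036; MMRM stayed near 0.025.
- Reversed (6.7% overall): 1 - Φ(1.96 + 0.17/1.23) = 0.018; simulated as low as 0.016.
- If every dropout has an early-termination visit: shift ±0.10, error 0.030 and 0.020.

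**The case against.** The strongest reply is that nothing formal depends on this. The step is labelled informal, the margin is fixed in advance, and SAP 8.6 reports the FVC interval whatever happens, so any reader can compare it with -1.1. The conclusion seldom changes. All of this stands, and it limits the point to a clarification.

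Because no visit is named, a reader might infer that the 6MWD test meant is the Week 26 key secondary, "Change from baseline to Week 26 in 6MWD", which is also an LOCF ANCOVA specified in SAP 8.6. The documents do not support that reading. The pair 6MWD and % predicted FVC heads Tables 6 and 7, where 6MWD is the Week 52 primary endpoint, and Table 6 specifies the LOCF ANCOVA at Week 52. FVC has only a Week 52 endpoint in the hierarchy.

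A reader might also infer that the SAP contradicts the protocol, or itself, over the key secondary method. It does not. Protocol 15.3.2.3.2 called for a method similar to the primary's, which was then ANCOVA. The SAP kept ANCOVA, and SAP 2 lets it supersede the protocol. The missing-data condition under which SAP 8.2 prefers MMRM is stated for 6MWD only, and a supportive MMRM is planned for every key secondary endpoint. What remains is that no reason is given for LOCF.

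**Conclusion.** The point holds as a minor matter of interpretation: the 6MWD half of the condition is not the test that decides 6MWD superiority. A reader might infer that family-wise error control is broken. It is not, because each gate-kept endpoint has one designated test and the non-inferiority reading lies outside the hierarchy.

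The sizes above are illustrations. They rest on small single-arm data (n = 10 for 6MWD, n = 9 for FVC), assumed correlations and Week 12 values, random dropout, and both tests having to fail. The base case assumes that dropouts have no early-termination visit, although SAP 6.3.2 requires one, so it leans slightly high.

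The preference for MMRM on the key secondary endpoints is weaker still. It brings no gain in type I error under balanced dropout, and nothing in the documents predicts the 12% against 4% split used to show one.

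**What to change.** Before database lock and while blinded, reword the sentence in SAP 8.6 so that:
- the 6MWD condition is failure of the primary MMRM test at Week 52;
- the FVC condition is failure of its designated Week 52 test;
- both must fail;
- the analysis that supplies the FVC 95% confidence interval is named.

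This changes only wording. It needs no new analysis and does not affect the sample size.

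Secondary, low-severity suggestion: consider making the planned MMRM on ITT-OBS the designated test for the key secondary endpoints, with LOCF ANCOVA as supportive, or else state why LOCF is kept. For Week 26 6MWD the primary model's own Week 26 contrast would serve, but SAP 8.5.1 now limits p-values to Week 52 and would need to allow one there. Because this changes which analysis is confirmatory, it needs a dated, blinded SAP revision. The analyses are already planned, and Appendix 3 gives sample code for both models. The downside is reliance on the missing-at-random assumption, which the primary analysis already makes.
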